## STUDY SYNOPSIS

**Protocol Title:** A phase II, open-label, trial of nivolumab, ipilimumab, and hypofractionated radiotherapy in adults with newly diagnosed, *MGMT* unmethylated glioblastoma

**NYU Protocol Number:** s17-00218

**BMS Study ID:** CA209-9JE

**IND:** 136853

**Principal Investigator/Sponsor:** [name], PhD

**Study Site:** NYU School of Medicine (NYUSoM)

**Investigational Products, Dose and Mode of Administration, Duration of Treatment with Investigational Products:**

- Nivolumab 3 mg/kg IV every 2 weeks for up to 2 years.
- Ipilimumab 1 mg/kg IV every 6 weeks for up to 2 years.
- Radiotherapy to a total dose of 45 Gy, given in 15 consecutive fractions of 3 Gy each fraction

**Study Phase:** II

**Research Hypothesis:** This study will test the hypothesis that hypofractionated radiotherapy (45 Gy in 15 fractions) will result in reduced treatment-induced severe lymphopenia and immunosuppression compared to standard chemoradiation and enhance the efficacy of combination immune checkpoint therapy to improve the overall survival of newly diagnosed *MGMT*-unmethylated glioblastoma (GBM) subjects.

CONFIDENTIAL

This material is the property of the NYU School of Medicine. Do not disclose or use except as authorized in writing by the study sponsor

**Objectives:**

*Primary*

- **Main Study Cohort:** To estimate the overall survival at 1 year (1-yr OS) of adults with newly diagnosed, *MGMT* unmethylated GBM administered nivolumab, ipilimumab and hypofractionated RT.
- **Surgical Study Cohort:** To assess Safety, Feasibility, and Tolerability of neoadjuvant ipilimumab and nivolumab (prior to tumor re-resection), and estimate rate of T-cell pathway induction.

*Secondary*

- **Main Study Cohort**
  - Assess safety and tolerability
  - Estimate additional measures of efficacy, including 2-year OS, median OS, median PFS, radiographic response rate, and median duration of response.
- **Surgical Study Cohort**
  - Estimate efficacy measures including 1-yr OS, 2-year OS, median OS, median PFS, radiographic response rate, and median duration of response.

*Exploratory*

- Assess association of 1-yr OS with: tumor tissue biomarkers including mutation burden, neoantigen load, immune marker expression [e.g. PD-L1, lymphocyte activation gene 3 (LAG3), indoleamine-2,3-dioxygenase (IDO) and T-cell immunoglobulin and mucin domain 3 (TIM3)], and PD-1+ tumor infiltrating lymphocytes (TILs).
- Assess association of 1-yr OS with baseline and change at 6 weeks in levels of circulating biomarkers, including: regulatory T cells ( $T_{reg}$ ); myeloid-derived suppressor cells (MDSC); and immune cell populations as profiled by high-parameter flow cytometry that simultaneously quantifies expression of proteins related to checkpoint inhibitors (PD1, CTLA4, TIM3, TIGIT, 41BB, CD150, LAG3, BTLA), differentiation status (CD45RA, CCR7, CD57, CD95, CD127), and other traits (CD25, IL12R, CXCR3, CXCR6).
- Evaluate effect of study regimen on total lymphocyte counts (TLC) and CD4 counts at fixed timepoints for up to 1 year compared to baseline.
- Explore whether sodium MRI, a non-invasive surrogate measure of cell death in tissue, can differentiate between treatment-related cell death/necrosis ("pseudoprogression") versus tumor progression and serve as a potential non-invasive pharmacodynamic biomarker.

CONFIDENTIAL

This material is the property of the NYU School of Medicine. Do not disclose or use except as authorized in writing by the study sponsor

### **Study Design:**

This is an open-label, phase II trial of nivolumab, ipilimumab and hypofractionated radiation therapy in adult patients with newly diagnosed, *MGMT* unmethylated GBM (confirmed centrally at NYU SoM) with the primary objective of determining the overall survival at 1 year.

**Safety Lead-In:** The study will start with a Safety Lead-In consisting of the first 6 subjects (Section 6.1) to further define the safety and tolerability of nivolumab and ipilimumab when given in combination with hypofractionated radiotherapy in previously untreated, newly diagnosed GBM patients with unmethylated *MGMT* promoter. Note, the patients enrolled in the Safety Lead-In cohort will subsequently be analyzed in the Main Study Cohort (see below). Also note, special safety provisions are included for the first 3 subjects enrolled (see Section 6.1.1). After the first 6 subjects are enrolled, enrollment will stop and subjects will be observed for 40 days for dose-limiting toxicities (DLTs). After all subjects in the Safety Lead-In cohort have completed the DLT observation period, the safety data will be reviewed by the Sponsor/Overall PI and the NYU DSMC. If 2 or more of the first 6 subjects in the Safety Lead-In experiences a DLT during the 28 day DLT observation period, the sponsor, with consultation from BMS and the FDA, may redesign the dosing and schedule of the study treatment or will stop the study for unacceptable toxicity. If 1 or fewer of the first 6 subjects experiences a DLT at the end of the 28 day DLT observation period, the study will continue enrollment onto the phase II part of the study.

**Main Study Cohort:** The Phase II trial is an open-label, one-stage phase II study and will enroll a total of 24 subjects, which includes the 6 subjects in the Safety Lead-In. A Bayesian monitoring approach will be applied to assess safety throughout the Phase II trial with pre-defined stopping rules.

**Surgical Study Cohort:** The Surgical Study Cohort will open once the Safety Lead-In is completed. We will use a single-stage design and enroll up to 16 subjects with newly diagnosed *MGMT*-unmethylated glioblastoma who are amenable to a larger resection will be included in this cohort.

CONFIDENTIAL

This material is the property of the NYU School of Medicine. Do not disclose or use except as authorized in writing by the study sponsor

### **Study Procedures:**

After screening procedures and registration, within 6 weeks of the first diagnostic surgery for glioblastoma, all subjects will initiate study treatment with one dose of nivolumab 3 mg/kg and one dose of ipilimumab 1mg/kg.

- Patients in the **Safety Lead-In/Main Study Cohort** will begin hypofractionated radiotherapy (HFRT) within 1 week of first nivolumab and ipilimumab dose.
- Patients in the **Surgical Study Cohort** (opens once Safety Lead-In completed) will undergo craniotomy and tumor re-resection within 2 weeks from the first dose of nivolumab and ipilimumab and begin HFRT 3 weeks following surgery

All subjects will receive HFRT to a total dose of 45 Gy, given in 15 consecutive fractions of 3 Gy each fraction.

All subjects will continue to receive nivolumab 3 mg/kg IV every 2 weeks and ipilimumab 1 mg/kg every 6 weeks from day of first nivolumab and ipilimumab administration. One treatment cycle will be defined as 42 days (6 weeks), corresponding to 3 doses of nivolumab and one dose of ipilimumab. Nivolumab and ipilimumab administration will continue for 2 years or until progression of disease, unacceptable toxicity, death, or another protocol criterion for subject withdrawal is met, whichever comes first.

Subjects will be evaluated every 8 weeks with radiographic imaging to assess response to treatment. The primary efficacy endpoint will be overall survival at 1 year. Disease assessments on study will be made using the Response Assessment for Neuro-Oncology (RANO) criteria. However, non-traditional Immunotherapy Response Assessment for Neuro-Oncology (iRANO) criteria may be considered for patient management. Adverse events will be monitored throughout the trial and graded in severity according to the guidelines outlined in the NCI Common Terminology Criteria for Adverse Events (CTCAE) version 4.03.

End of treatment assessments will be performed within 7 days after last drug administration or within 7 days after decision to end treatment. Site visits and safety laboratories are to be performed at 30 days ( $\pm 7$  days) and 90 days ( $\pm 14$  days) after the last study drug is given, unless the subject is unable to travel due to deteriorating medical condition, due to the potential risk for delayed immune-related toxicities. Post-treatment, all participants will be followed until resolution or stabilization of any serious or reportable adverse events occurring during treatment or starting within 30 days of last study drug. Assessments may continue for ongoing reportable adverse events.

Subjects who discontinue study drug must continue to be followed for collection of outcome and/or survival follow-up data until death, withdrawal of permission to record at least survival data, or subject is lost to follow-up.

Following the 90-day post-drug visit, all subjects will be contacted every 3 months ( $\pm 14$  days) to assess for study-treatment related toxicities, initiation of any new anti-cancer treatments, and survival status. Contact may be performed by a site visit, telephone contact, e-mail, or mail.

### **Study Population:**

#### *Inclusion Criteria:*

1. Male or female subjects aged  $\geq 18$  years.

CONFIDENTIAL

This material is the property of the NYU School of Medicine. Do not disclose or use except as authorized in writing by the study sponsor

2. Histopathological evidence of glioblastoma or gliosarcoma, WHO grade IV.
3. Tumor *MGMT* promoter DNA not methylated (i.e., unmethylated) by central testing.
4. There will be two study cohorts:
  - a. **Main Study Cohort:** Maximal tumor diameter (including residual tumor and resection cavity if subjects had tumor resection rather than only stereotactic biopsy) of 6.6 cm or less. Maximal tumor size allowed is derived from an estimated maximal radiotherapy planning target volume (PTV) of 150 cm^3. Note, the maximal tumor diameter for the first 3 subjects enrolled will be 5 cm.
  - b. **Surgical Study Cohort:** Patients who received tumor biopsy or subtotal tumor resection and are amenable to a second tumor resection with expected post-operative tumor diameter of ≤ 6 cm (PTV of ≤ 150 cm^3)
5. Subjects must not have received any prior standard or investigational anti-tumor therapy other than surgery and must not intend to receive any standard or investigational anti-tumor therapy other than the study regimen.
6. Karnofsky performance status (Appendix 2) of ≥60.
7. Availability of a paraffin-embedded or frozen tumor-tissue block with a minimum of 1 cm^2 of tumor surface area, or 20 unstained slides from the glioblastoma tissue specimen if a tumor block cannot be submitted. **For Surgical Study Cohort:** availability of pre- and post-operative tumor tissue is required.
8. Subjects must start study agent within 6 weeks from the first diagnostic surgery for glioblastoma.
9. Begin of treatment with study agent:
  - **Main Study Cohort:** Subjects must start study agents no sooner than 2 weeks from last surgical resection and 1 week for stereotactic biopsy.
  - **Surgical Study Cohort:** Subjects must receive 1st dose of study agents 2 weeks prior to tumor re-resection and must resume study agents no sooner than 2 weeks from date of tumor re-resection.
10. A contrast-enhanced MRI must be obtained within 21 days of the first dose of study treatment.
11. Adequate hematologic, hepatic, and renal function defined by
  - a. White blood cell count ≥ 2.0 × 10^9/L
  - b. Absolute neutrophil count ≥ 1.5 × 10^9/L
  - c. Platelet count ≥ 100 × 10^9/L
  - d. Hemoglobin > 9 g/dL
  - e. Serum creatinine ≤ 1.5 × upper limit of normal (ULN) or creatinine clearance (CrCl) ≥ 40 mL/min according to the Cockcroft-Gault formula or local institutional standard method
  - f. Aspartate aminotransferase (AST) and alanine aminotransferase (ALT) ≤ 3 × ULN
  - g. Total bilirubin ≤ 1.5 × ULN (except subjects with Gilbert Syndrome, who can have total bilirubin < 3.0 mg/dL)
12. Women of child-bearing potential (WOCBP) and men able to father a child must agree to use highly effective contraception (any contraceptive method with a failure rate of less than 1% per year) while on study drug and for 23 weeks (for women) or 31 weeks (for men) after the last dose of study drug.
  - a. WOCBP must have a negative serum or urine pregnancy test within 24 hours of initiation of study drug.

CONFIDENTIAL

This material is the property of the NYU School of Medicine. Do not disclose or use except as authorized in writing by the study sponsor

- b. WOCBP is defined as any female who has experienced menarche and who has not undergone surgical sterilization (hysterectomy or bilateral oophorectomy) or who is not postmenopausal. Menopause is defined clinically as 12 months of amenorrhea in a woman over 45 in the absence of other biological or physiological causes. In addition, women under the age of 55 must have a documented serum follicle stimulating hormone (FSH) level less than 40 mIU/mL to be defined as post-menopausal.
- c. WOCBP receiving nivolumab will be instructed to adhere to contraception for a period of 23 weeks after the last dose of investigational product. Men receiving nivolumab and who are sexually active with WOCBP will be instructed to adhere to contraception for a period of 31 weeks after the last dose of investigational product. These durations have been calculated using the upper limit of the half-life for nivolumab (25 days) and are based on the protocol requirement that WOCBP use contraception for 5 half-lives plus 30 days and men who are sexually active with WOCBP use contraception for 5 half-lives plus 90 days.
- d. Highly effective contraceptive measures include: stable use of oral contraceptives such as combined estrogen and progestogen and progestogen only hormonal contraception or other prescription pharmaceutical contraceptives for 2 or more menstrual cycles prior to screening; intrauterine device [IUD]; intrauterine hormone-releasing system (IUS); bilateral tubal ligation; vasectomy and sexual abstinence.
- e. Contraception is not required for men with documented vasectomy.
- f. Pregnancy testing and contraception are not required for women with documented hysterectomy or tubal ligation.
- g. Women must not be breastfeeding.

13. Willing to and capable of providing written informed consent prior to any study related procedures.

14. Ability and willingness to comply with all study requirements, including scheduled visits, treatment plans, laboratory tests, and other study-related procedures.

#### *Exclusion Criteria*

- 15. Prior use of any standard or investigational anti-tumor therapy other than surgery
- 16. Planned participation in another study of an investigational agent or investigational device or planned use of any other agent or therapeutic device intended for therapy of glioma.
- 17. Infratentorial tumors.
- 18. Patients with >1 cm midline shift on postoperative, baseline brain MRI.
- 19. Diffuse leptomeningeal gliomatosis.
- 20. Known mutation of the *IDH1* or *IDH2* genes in the tumor, since glioblastomas with these mutations have different biology and are associated with improved prognosis.
  - a. Documentation that no *IDH1* or *IDH2* mutations are present in the tumor by a CLIA approved laboratory is required prior to initiation of study treatment.
- 21. Intracranial hemorrhage grade >1 not attributable to recent neurosurgery.
- 22. Systemic treatment with either immunosuppressive doses of corticosteroids (> 10 mg daily prednisone equivalents) or other immunosuppressive medications within 14 days of study drug administration.
  - a. Subjects on a standard high-dose steroid taper after craniotomy or stereotactic biopsy may have received a higher dose of corticosteroids within 14 days of registration,

CONFIDENTIAL

This material is the property of the NYU School of Medicine. Do not disclose or use except as authorized in writing by the study sponsor

however must be at a dose < 10 mg daily prednisone or bioequivalent per day within 5 days prior to initiation of study drug.

- b. Administration of steroids through a route known to result in a minimal systemic exposure [i.e., intranasal, intraocular, inhaled, topical, or local injection (e.g., intra-articular injection) corticosteroids (<5% of body surface area)] are permitted in the absence of active autoimmune disease.
- c. Subjects requiring adrenal replacement with corticosteroids are eligible if the steroids are at doses ≤ 10 mg prednisone or bioequivalent per day in the absence of active autoimmune disease.
- d. Steroids as premedication for hypersensitivity reactions (e.g., CT scan premedication) are allowed.

23. Active autoimmune disease that might deteriorate when receiving an immuno-stimulatory agent. The following conditions are not exclusions (subjects with the following conditions are permitted):

- a. Patients with diabetes type I, vitiligo, residual hypo- or hyperthyroidism due to autoimmune condition only requiring hormone replacement, or psoriasis not requiring systemic immunosuppressive treatment, or autoimmune conditions not expected to recur in the absence of an external trigger.

24. Prior organ transplantation, including allogeneic stem cell transplantation.

25. Known history of, or any evidence of active, non-infectious pneumonitis within the last 5 years.

26. Known severe (NCI-CTCAE v4.03 Grade 3 or 4) infusion-related allergy or acute hypersensitivity reaction attributed to any monoclonal antibody, any history of anaphylaxis, or uncontrolled asthma (that is, 3 or more features of partially controlled asthma).

27. Unable tolerate an MRI, or have a contraindication to MRI.

28. Active infection requiring systemic therapy.

29. Known history of testing positive for human immunodeficiency virus (HIV) or known acquired immunodeficiency syndrome.

30. Positive test for hepatitis B virus surface antigen (HBV sAg) or hepatitis C virus (HCV antibody) indicating acute or chronic infection.

31. Vaccination within 4 weeks of the first dose of study drug and while on trials is prohibited except for administration of inactivated vaccines. Note: Seasonal influenza vaccines for injection are generally inactivated flu vaccines and are allowed; however intranasal influenza vaccines (e.g., Flu-Mist®) are live attenuated vaccines, and are not allowed.

32. Clinically significant (i.e., active) cardiovascular disease: cerebral vascular accident/stroke (< 6 months prior to enrollment), myocardial infarction (< 6 months prior to enrollment), unstable angina, congestive heart failure ( $\geq$  New York Heart Association Classification Class II), or serious cardiac arrhythmia requiring medication.

33. Patients with another active cancer [excluding basal cell carcinoma, cervical carcinoma in situ or melanoma in situ]. Prior history of other cancer is allowed, as long as there was no active disease within the prior 2 years.

34. All other unstable, severe, or chronic medical or psychiatric conditions including colitis, inflammatory bowel disease, pneumonitis, pulmonary fibrosis, recent (within the past year) or active suicidal ideation or behavior, known alcohol or drug abuse, or laboratory abnormalities that may increase the risk associated with study participation or study treatment administration or may interfere with the interpretation of study results and, in the judgment of the investigator, would make the patient inappropriate for entry into this study.

CONFIDENTIAL

This material is the property of the NYU School of Medicine. Do not disclose or use except as authorized in writing by the study sponsor

## **Study Assessments:**

### *Efficacy*

Efficacy assessment consisting of a contrast-enhanced brain MRI will be performed every 8 weeks on study,  $\pm 7$  days, until disease progression is documented or treatment is discontinued (whichever occurs later). Response Assessments will be performed on every brain imaging assessment performed on protocol per RANO criteria.

### *Safety*

Subjects will be evaluated for safety if they have received any study drug. Toxicity assessments will be continuous during the treatment phase. Once subjects reach the survival follow-up phase, either in person or documented telephone calls to assess the subject's status are acceptable. Adverse events and laboratory values will be graded according to the NCI-CTCAE version 4.03.

## **Statistical Considerations:**

All subjects who receive at least 1 dose of ipilimumab and nivolumab will be included in the primary analysis (1yr-OS) of the phase II study.

### *Sample Size:*

**Main Study Cohort:** Based on historical measures, a 12 month (1yr-OS) of 35% will be considered non-promising; an increase in the 1yr-OS to 60% will be considered promising. We will use a single-stage design and enroll 24 patients. This will provide 80% power to detect an increase in the 1-year OS from 35% to 60%, using a 0.05-level test.

**Surgical Study Cohort:** Based on historical measures, a T-cell pathway induction rate of 33% will be considered non-promising; an increase in the T-cell pathway induction rate to 64% will be considered promising. We will use a single-stage design and enroll 16 patients. This will provide 80% power to detect an increase in the 1-year OS from 33% to 64%, using a 0.05-level test.

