#### **Surgical Study Cohort:**

- The primary objective is safety, feasibility and tolerability

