## 7 Statistical Plan

### 7.1 Background for Statistical Plan

*MGMT* unmethylated, elderly and poor functional status newly diagnosed GBM patients treated on recent randomized clinical trials with regimens including radiotherapy, temozolamide or bevacizumab have median survivals in the range of 6-12 months, with one study that did not enroll patients with unresectable (biopsy-only) tumors which carry poorer prognosis reporting 14 months. With standard chemoradiation, the fraction of patients alive at 1 and 2 years for *MGMT* unmethylated patients aged 70 or less with good functional status are 50% and 6%. The 1 year OS proportion for elderly and poor prognosis patients ranges from 21-32%.

With regards to hypofractionated radiotherapy in newly diagnosed GBM, the IAEA randomized trial treated elderly and poor functional status GBM patients aged  $\geq 50$  with hypofractionated RT (5 fraction) and the median OS was 8 months. In recent years, other small phase I and II studies have reported short course RT to have similar efficacy similar to standard treatment regimens in selected newly diagnosed GBM patients, although these studies did not stratify by *MGMT* methylation status. Median OS in these *MGMT* non-stratified studies ranged from 15 to 20 months.

Based on these historical measures, a 12 month (1yr-OS) of 35% will be considered non-promising in *MGMT* unmethylated, newly diagnosed GBM subjects; an increase in the 1yr-OS to 60% will be considered promising.

Most recently, a phase II randomized multicenter clinical study in patients with recurrent glioblastoma suggest that treatment with the PD-1 inhibitor pembrolizumab results in significantly prolonged overall survival when given neoadjuvantly (prior to tumor re-resection) as compared to pembrolizumab adjuvantly (after tumor re-resection). This increase in overall survival was associated with upregulated T cell-activation and Interferon- $\gamma$ -gene expression signatures and downregulation of cell-cycle related gene expression signatures in tumor cells. In this study, interferon- and T cell-pathway induction was seen in 9 of 14 tumors (64%) from patients who received neoadjuvant pembrolizumab compared to 5 of 15 tumors (33%) from patients who received pembrolizumab adjuvant-only.

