### 7.2.3 Phase II trial – Surgical Study Cohort

A single-stage design will be utilized to estimate overall survival, with a hypothesized rate of T-cell pathway induction of 64%= $H_1$  and 33%= $H_0$ . We will enroll 16 patients; this design has a two-sided Type I error of 0.05 and a power of 80%.

CONFIDENTIAL

This material is the property of the NYU School of Medicine. Do not disclose or use except as authorized in writing by the study sponsor

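### The surgical cohort's power statement names survival, but its 33% and 64% are T-cell pathway induction rates, an endpoint missing from Sections 2.2 and 3.2

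*Combined protocol and SAP*

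**What the plan says.** The synopsis (Statistical Considerations, Sample Size) first sets the surgical cohort's benchmarks: "a T-cell pathway induction rate of 33% will be considered non-promising", and "an increase in the T-cell pathway induction rate to 64% will be considered promising". With 16 patients in a single stage, it then concludes: "This will provide 80% power to detect an increase in the 1-year OS from 33% to 64" per cent, with a test at the 0.05 level.

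Section 7.1 gives the origin of the figures. In a randomised trial of neoadjuvant pembrolizumab in recurrent glioblastoma, "interferon- and T cell-pathway induction was seen in 9 of 14 tumors (64%) from patients who received neoadjuvant pembrolizumab", against 5 of 15 (33%) in the adjuvant-only group.

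Section 7.2.3 opens: "A single-stage design will be utilized to estimate overall survival, with a hypothesized rate of T-cell pathway induction" of 64% under the alternative and 33% under the null. It enrols 16 patients and states a two-sided Type I error of 0.05 with 80% power.

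The endpoint lists differ. The synopsis objectives put safety, feasibility and tolerability first and add "estimate rate of T-cell pathway induction", all under the primary heading. Section 3.2 has only: "The primary objective is safety, feasibility and tolerability". Section 2.2 matches Section 3.2. Induction is in neither Section 3.3 nor Section 3.4. For this cohort 1-year OS is a secondary measure, both in the synopsis and in Section 3.3.

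**The concern.** A power statement should tell the reader which outcome the sample size was built for. Here the sentence that carries the 80% names a secondary outcome for which this cohort has no null and no alternative. The outcome that does set the sample size is missing from the body's objectives and endpoints.

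Two things are at stake. Taken literally, the sentence presents the cohort as a powered survival comparison, which it is not. Conversely, Sections 2.2 to 3.4 do not commit the study to the hypothesis that justifies 16 patients, so induction could be promoted or demoted after the results are known and some part of the protocol could be cited in support.

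**Working it through.** **Which outcome do the rates belong to?** 5/15 = 33.3% and 9/14 = 64.3%, both counts of tumours with pathway induction (Section 7.1). Neither figure is used anywhere as a survival benchmark. The plan's 1-year OS benchmarks are 35% and 60%, set for the 24-patient main cohort (Sections 7.1 and 7.2.2). So the hypotheses concern induction, and the survival wording is the error.

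**Does the stated 80% reproduce for induction?** Inputs: n = 16, p0 = 0.33, p1 = 0.64, single arm, single stage (synopsis and Section 7.2.3). For a cutoff r, with X binomial:

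- alpha(r) = P(X ≥ r | n, p0) = Σ from k = r to n of C(n,k) p0^k (1 − p0)^(n − k)
- power(r) = P(X ≥ r | n, p1)

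| Success if at least | Upper-tail alpha | Power |
|---|---|---|
| 8 of 16 | 0.1205 | 0.9209 |
| 9 of 16 | 0.0470 | 0.8187 |
| 10 of 16 | 0.0148 | 0.6572 |

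*One-sided 0.05.* The smallest cutoff with alpha at or below 0.05 is 9, with power 81.9%. The 80% reproduces. One-sided normal approximations agree broadly: arcsine 81.0%, Wald 82.6%, score 83.5%, continuity-corrected 76.2%.

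*Two-sided 0.05, allowing 0.025 in the upper tail.* A cutoff of 9 fails because 0.0470 exceeds 0.025. The cutoff becomes 10, with power 65.7%. Two-sided approximations give arcsine 71.3%, Wald 73.4%, score 74.6% and continuity-corrected 65.7%. None reaches 80%.

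*Sensitivity to rounding.* With 5/15 and 9/14 unrounded, a cutoff of 9 has alpha 0.04996 and power 82.5%, and a cutoff of 10 has alpha 0.0159 and power 66.6%. The conclusions do not change.

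*Sample size if two-sided 0.05 is kept.* Exact power is 58.5% at n = 17, 69.7% at 18, 78.8% at 19, 73.2% at 20 and 81.2% at 21 (success at 12 or more, upper tail 0.0195). The smallest n with at least 80% is 21.

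Replacing the outcome name in the synopsis therefore changes no number there, since the synopsis leaves sidedness open. Doing the same in Section 7.2.3 leaves a two-sided error rate beside a power that 16 patients do not give.

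**The case against.** The best defence is that the intended outcome can be recovered. The sample-size paragraph names induction twice just before the slip, Section 7.1 explains both rates, Section 7.2.3 puts the null and alternative on induction, and the synopsis objectives list it as primary. A careful analyst is unlikely to run a powered survival test in these 16 patients. On that view this is an editorial slip with a correct number behind it.

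Much of that stands. The 80% is right for a one-sided test of induction, and the endpoint is inconsistent across sections rather than absent from the protocol. It does not dispose of the point, because the slip occurs in both places where the design is stated, one of them the governing statistical section. The reader also has to override the text of Sections 2.2 and 3.2 to reach the intended reading.

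Two stronger readings are tempting and are not supported. A reader might apply the main cohort's 35% and 60% to 16 surgical patients and conclude that the cohort loses power for survival. No section plans such a test or gives this cohort survival hypotheses, so there is no planned power to lose. A reader might also infer that the only powered claim in the protocol names the wrong outcome. The main cohort has its own powered hypothesis in Section 7.2.2, and the surgical hypotheses in Section 7.2.3 are on induction.

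**Conclusion.** The point holds as an internal inconsistency. The outcome is mislabelled in the synopsis power sentence and in the opening of Section 7.2.3, and the endpoint that sets the sample size is missing from Sections 2.2, 3.2, 3.3 and 3.4 although the synopsis makes it primary. It should be corrected. The endpoint mismatch gives it more weight than a typing error would have.

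The numerical consequence is confined to Section 7.2.3: for induction at n = 16, power is 81.9% one-sided and 65.7% two-sided, against the 80% stated as two-sided. These figures assume an exact binomial test, 0.025 in the upper tail for the two-sided case, and all 16 patients evaluable for induction. The documents state no dropout allowance and none was applied.

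**What to change.** 1. In the synopsis sample-size paragraph, replace 1-year OS with the T-cell pathway induction rate. In Section 7.2.3, do the same for overall survival.
2. List the induction rate as a primary endpoint of the surgical cohort in Sections 2.2 and 3.2, matching the synopsis objectives.
3. State that surgical 1-year OS is estimated with a confidence interval and is not tested.
4. In Section 7.2.3, either state a one-sided 0.05 test (success at 9 or more of 16, exact alpha 0.047, power 81.9%) or keep two-sided 0.05 and restate the power as about 66% (10 or more of 16). Holding 80% with a two-sided test would need 21 patients. Make the synopsis state the same sidedness.

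Items 1 to 3 are wording. Item 4 needs a decision on the error rate but no extra patients unless 80% two-sided power is wanted. Listing induction as primary also calls for a rule on when a tumour counts as induced and for the success cutoff. I found neither in the documents, and both should be fixed before the tissue results are seen.
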